#### **11.5.5.1 Solicited Adverse Events**

Solicited events will be summarized by computing the proportion of participants with observation of any event, and any event according to event type, over all vaccinations within groups, and for each vaccination individually within group. Additional analyses will summarize the frequency and duration of events ongoing at Day 7 post-study vaccine administration. Summaries will be prepared corresponding to maximum severity and duration per participant, where relevant. Solicited adverse event rates will be accompanied by two-sided exact 95% confidence intervals. Within cohorts (separately for each type), the rate of solicited adverse events will be compared using a two-sided Fisher's exact test for pairwise comparisons, both overall and by type following each dose, and overall (across doses); this will be repeated for severe and for moderate or greater events.

#### **11.5.5.2 Unsolicited Adverse Events**

All unsolicited adverse events will be listed and summarized in tables. Unless an AE is classified as an SAE, summaries of unsolicited AEs will be made using only those events recorded with onset within 28 days of the prior vaccine dose. Unsolicited adverse events will primarily be summarized on the participant level, where a participant contributes once to a given event type under the maximum severity and/or causality, as appropriate. Tables will additionally display the number of events of a given type observed within a group, regardless of the number of participants from which they originate.

Unsolicited adverse events will be summarized by severity and by relationship; SAEs will be summarized overall, and by reason for seriousness designation. In addition, all AEs, coded with MedDRA, will be summarized by System Organ Class (SOC) and Preferred Term (PT), and separate tables by SOC and PT will be prepared for severe unsolicited AEs, severe AEs, related AEs, severe related AEs, and SAEs. A table will be prepared summarizing all preferred terms occurring in  $\geq 2\%$  of participants. Additional summaries will include the rate of participants experiencing an AE leading to withdrawal from vaccinations, or from the study. Additional listings will be prepared for severe AEs, related AEs, and SAEs. Within OPV type, the rates of participants experiencing severe adverse events, related adverse events, and serious adverse events will be compared across groups using a two-sided Fisher's exact test for pairwise comparisons.

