## 2.3 Study Endpoints

### 2.3.1 Primary Endpoints:

#### Safety

- Frequency of serious adverse events (SAEs) from Day 1 study vaccination through the end of the study

- Frequency of solicited adverse events (AEs) for 7 days (day of study vaccination and 6 following days) after each dose of study vaccine
- Frequency of unsolicited AEs for 28 days (day of study vaccination and 27 following days) after each dose of study vaccine [including clinically significant aberrant safety monitoring laboratory values on Day 8 reported as AEs]

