**Unsolicited AEs** are any AEs reported spontaneously by the participant, observed by the study personnel during study visits or those identified during review of medical records or source documents.

In the absence of a diagnosis, abnormal physical examination findings or abnormal clinical safety laboratory test results that are assessed by the investigator to be clinically significant will be reported as an AE.

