## 8.2 Reporting Period and Parameter

Safety events are reported from the time of signing the ICF through each participant's completion of the study 168 days after their Day 1 study vaccination. Specifically, solicited AEs will be collected for 7 days (day of study vaccination and 6 following days) after each dose of study vaccine. If a solicited AE started during the 7 days post-vaccination and continues beyond the 7 days, it will continue to be reported as a solicited AE. Unsolicited AEs will be collected for 28 days (day of study vaccination and 27 following days) after each dose of study vaccine. SAEs will be collected from Day 1 study vaccination through the end of the study (Day 169 Telephone visit).

Any untoward medical occurrence after signing the ICF but before receipt of study vaccine, although not to be reported as an AE, if it is assessed as related to participation in the study, must still be reported by email to PATH within 3 days of awareness.

Due to uncertainties around the COVID-19 pandemic and the potential for stay-at-home orders, if a subject is unable to come to the clinic for a visit, the scheduled and applicable safety assessments may be conducted by telephone.

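### The 28-day limit on unsolicited-AE summaries exempts SAEs, so SAEs with onset up to Day 169 can enter tables meant for a 28-day primary endpoint

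*Protocol*

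**What the plan says.** Section 2.3.1 sets out separate primary safety endpoints. One is "Frequency of unsolicited AEs for 28 days (day of study vaccination and 27 following days) after each dose of study vaccine". Another is "Frequency of serious adverse events (SAEs) from Day 1 study vaccination through the end of the study". Section 8.2 collects data on the same two schedules: "Unsolicited AEs will be collected for 28 days (day of study vaccination and 27 following days) after each dose of study vaccine", and SAEs from Day 1 through the Day 169 telephone visit.

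The analysis rule is in section 11.5.5.2: "Unless an AE is classified as an SAE, summaries of unsolicited AEs will be made using only those events recorded with onset within 28 days". The limit is counted from the preceding dose. The same section adds that "SAEs will be summarized overall, and by reason for seriousness designation" and that "separate tables by SOC and PT will be prepared for severe unsolicited AEs, severe AEs, related AEs, severe related AEs, and SAEs".

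Section 8.1.1 defines unsolicited AEs without reference to seriousness: they "are any AEs reported spontaneously by the participant, observed by the study personnel during study visits", or are found on review of records. An SAE can therefore be an unsolicited AE.

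**The concern.** The subject of the rule in section 11.5.5.2 is the unsolicited-AE summaries, and serious events are carved out of their time limit. No sentence confines SAEs with onset after the window to the SAE tables. Taken at its word, the rule lets an SAE with onset on, say, Day 150 count in the any-AE, severe and related unsolicited tables. The endpoint those tables would naturally be used to report stops 27 days after each dose.

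Once the window closes, non-serious unsolicited AEs are no longer collected. A table built on the rule would therefore combine complete ascertainment over a short period with SAE-only ascertainment over a long one, and its rate would not be the rate the endpoint defines. The period outside the window also differs between the one-dose and two-dose cohorts, which section 11.5.5 pools within vaccine type.

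Safety is the only primary objective, the trial is first-in-human, and groups can be as small as 15. Two programmers should not be able to build different primary safety tables from the same sentence.

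There is also a small edge difference. A limit of 28 days from the prior dose can be read as reaching Study Day 29, whereas the endpoint stops at Study Day 28. In the two-dose cohorts Day 29 is the day of the second dose.

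**Working it through.** **1. The two rules side by side.** Endpoint (sections 2.3.1 and 8.2): vaccination day plus 27 days after each dose, serious or not. Analysis rule (section 11.5.5.2): about 28 days for non-serious events, no limit for serious events. They agree for non-serious events, apart from the edge day, and differ for every SAE with onset after the window.

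**2. Time outside the window, to Day 169.** Schedule from sections 3 and 8.2, with dose 2 on Day 29.
- One dose (Cohorts 1 and 3): 169 − 28 = 141 days.
- Two doses (Cohorts 2 and 4): 169 − 56 = 113 days.

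**3. The plan's own precision table (section 11.3).** For n = 70 it gives a minimum detectable rate of 4.2%, an exact 95% interval of (0.0, 5.1) with no events and (0.04, 7.7) with one. Recomputed: 1 − 0.05^(1/70) = 4.19%; Clopper-Pearson limits (0, 5.13) and (0.036, 7.70). The row reproduces. This point does not depend on the table, but the table shows what one counted event does. At n = 15 the stated interval moves from (0.0, 21.8) to (0.1, 31.9).

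**4. Effect of one late SAE.** If the participant has no in-window event of that category, the proportion rises by 1/n: 1/70 = 1.4 points, 1/50 = 2.0, 1/20 = 5.0, 1/15 = 6.7. If the participant already counts, it does not change.

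**5. Expected number of late SAEs.** The protocol gives no SAE rate, so an incidence r of 1% to 8% per person-year is assumed for illustration. Expected number = r × (n₁ × 141 + n₂ × 113)/365.25, where n₁ and n₂ are the one-dose and two-dose participants.
- Pooled nOPV at maximum size, 20 + 50 = 70: (2,820 + 5,650)/365.25 = 23.19 person-years.
- Pooled mOPV at maximum size, 20 + 25 = 45: (2,820 + 2,825)/365.25 = 15.46 person-years.

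| Assumed r | Late SAEs, nOPV | Points, nOPV | Points, mOPV | Difference |
|---|---|---|---|---|
| 1% | 0.23 | 0.33 | 0.34 | −0.01 |
| 2% | 0.46 | 0.66 | 0.69 | −0.02 |
| 4% | 0.93 | 1.33 | 1.37 | −0.05 |
| 8% | 1.86 | 2.65 | 2.75 | −0.10 |

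At the minimum sizes (45 and 30) the difference is also about −0.10 point at 8%. These figures assume each late SAE falls in a different participant with no in-window event. If instead 30% of participants already had an in-window event (also an assumption), the addition to the any-AE rate in the nOPV arm is 0.7 times as large: 0.23 points at 1% and 1.86 at 8%.

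**6. Arms within a cohort.** Both arms have the same doses and follow-up, so the time outside the window is the same. The pooled difference in step 5 arises only because the one-dose and two-dose cohorts are mixed differently under 1:1 and 2:1 allocation.

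**The case against.** The strongest reply is that the clause is protective. Section 11.5.5.2 is where the SAE analyses are described, and without the exemption a 28-day filter would delete late SAEs whose own endpoint runs to end of study. The section also orders SAE summaries, an SAE table by SOC and PT, SAE listings and an SAE comparison. It labels no table as the estimate of the 28-day endpoint, and section 11.5.1 leaves further detail to the SAP. This reading is plausible, and it stands as a possible intent. It is not what the sentence says, however: the exemption sits inside the rule for unsolicited-AE summaries, and nothing keeps late SAEs out of them.

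A second reply also has force. Keeping late SAEs in the related and severe tables is a defensible caution for a live vaccine, and simply removing them could hide a late related SAE. The fix has to meet this.

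A reader might go further and infer that the primary any and severe rates are inflated, perhaps by a large relative amount in the severe table and its Fisher tests. The document does not support that:
- Seriousness (section 8.1.3) and severity (section 8.3) are defined separately. Life-threatening and fatal events must be reported as SAEs, but a hospitalization need not be severe.
- The Fisher comparison is specified for severe, related and serious adverse events. The section lists severe unsolicited AEs and severe AEs as different tables, so the tested severe rate is not stated to be the 28-day endpoint.
- A relative overstatement requires an SAE rate and a severe-AE rate, and the protocol gives neither.
- The absence of a non-serious event on, say, Day 40 in a one-dose cohort follows from the collection rule in section 8.2, not from the analysis sentence.

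The edge-day difference is slight, since sections 2.3.1 and 8.2 already define 28 days as the vaccination day plus 27.

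**Conclusion.** The point holds as a mismatch between an analysis rule and the primary endpoint it serves. As written, SAEs with onset up to Day 169 can be counted in unsolicited-AE summaries, while the endpoint is confined to 28 days after each dose. Each such SAE in a participant with no in-window event adds 1.4 points at n = 70 and up to 6.7 at n = 15. On assumed rates of 1% to 8% per year, fewer than two are expected among 70 nOPV recipients, and the pooled difference between arms moves by about 0.1 point at most.

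The weight is minor. What is affected is the meaning of the absolute rate. Inflation of the reported rates is not demonstrated, and the randomized comparison within a cohort is not biased, because follow-up is the same in both arms.

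**What to change.** Amend section 11.5.5.2 in two statements:

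1. The summaries that estimate the 28-day unsolicited-AE endpoint include all unsolicited AEs, serious or not, with onset from the day of vaccination through the 27 following days after each dose. This replaces the limit of 28 days from the prior dose and removes the SAE exemption from these summaries.
2. SAEs with onset from Day 1 through Day 169 are summarized separately, including by severity and by relationship, so that late related SAEs remain visible.

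If tables of all severe or all related AEs are meant to cover the whole study, give that period in their titles. The cost is a short wording change and an onset filter in the table programs. Data collection and SAE reporting do not change. If the change is made in the SAP instead, section 11.5.3 requires it to be described and justified there and in the clinical study report.

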#### **11.5.5.3 Safety Labs**

Each continuous hematology and chemistry laboratory test will be evaluated by means of descriptive statistics (i.e., number of participants, mean, SD, median, minimum, and maximum) on the actual values,

at each assessment time point and by group. Changes from baseline will also be summarized by assessment time point and by group.

Clinical safety laboratory test values will be evaluated according to the table for grading the severity of adverse events provided in this protocol or in accordance with the normal ranges of the clinical laboratory (below, within, or above normal range) for parameters for which no toxicity grades are defined.

Clinical laboratory abnormalities will be summarized by group, parameter, time point, and grade, including the maximum grade post-baseline abnormality for each participant for each parameter. Summaries will include any baseline abnormality across parameters within group, and any post-baseline abnormality across visits within parameters, as well as across parameters and visits. Abnormalities will also be summarized in a shift table, displaying the frequency of post-baseline abnormalities by grade (with separate categories for high and for low values of a given lab, where relevant) cross-tabulated with the baseline classification for each time point for each lab. Boxplots will display the raw value by lab parameter and study collection day and will include separate symbols to depict values out of range, and those that are grade 2 or higher.

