### **6.2.2 First Vaccination Visit – Day 1 Visit**

Prior to Vaccine Administration

- Review concomitant medications
- Review inclusion/exclusion criteria and ensure continued eligibility for study vaccination, including absence of symptoms that may confound later safety and solicited AE assessments
- If any interim symptoms, perform a targeted physical examination
- Measure vital signs

- For females of childbearing potential (FOCB), assess and document continuing use of contraceptives and perform urine pregnancy test
- Collect venous blood samples (approximately 15 mL) for
  - CBC, including hemoglobin, hematocrit, WBC count, neutrophil count, lymphocyte count, eosinophil count, and platelet count
  - Serum chemistries to include creatinine, ALT, and total bilirubin
- If not done earlier than Day 1, once eligibility is confirmed, randomize participant

Clinical safety laboratory test results used to determine participant eligibility will be those obtained at screening, but the Day 1 test results will be used as baseline for analyses.

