## 7.2 Clinical Laboratory Tests

Protocol mandated clinical screening and safety laboratory tests will be conducted in real time by site local laboratories that are properly accredited and subscribed to a proficiency testing program. These tests include:

- CBC: hemoglobin, hematocrit, WBC count, neutrophil count, lymphocyte count, eosinophil count, and platelet count, performed at screening, and at Day 1 and Day 8 visits
- Serum Chemistry: ALT, total bilirubin, and creatinine, performed at screening, and at Day 1 and Day 8 visits
- Pregnancy test: Serum  $\beta$ -HCG at screening, then urine  $\beta$ -HCG prior to each study vaccination (conducted on site)
- Human immunodeficiency viruses 1 and 2 (HIV 1/2) infection testing performed at screening
- Hepatitis B virus surface antigen performed at screening (HBsAg)
- Hepatitis C virus antibody (HCV Ab), if positive, HCV PCR, performed at screening
- Total IgG and IgA performed at screening

Laboratory results will be reviewed promptly by the investigator. Participants will be notified of any clinically significant abnormalities. If clinically significant abnormalities are identified during screening, participants will be referred to their primary health provider or appropriate medical center. If identified during the study, participants may be asked to return to the study site for further evaluation, including clinical evaluation and repeat laboratory testing (e.g., monitoring for resolution or stabilization) as warranted. Any test may be repeated for test results determined to be spurious by the investigator (e.g., following improper specimen collection) or if a valid test cannot be performed on the original blood collected (e.g., collection tube broken during transportation).

The immunological assays to be performed include:

- Serum neutralizing antibodies to type-specific polioviruses at screening and 28 days after each vaccine dose, to be performed at the Polio and Picornavirus Laboratory Branch at the CDC (for screening purposes [eligibility determination] only, baseline assays will be performed at a commercial qualified laboratory, Quest Diagnostics)

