**Abnormal clinical safety laboratory test results reported as AEs:**

The severity of abnormal clinical safety laboratory test results reported as AEs will be graded based on the grading scale in [Table 5](#) below. The table is adapted from the FDA Guidance for Industry: Toxicity Grading Scale for Healthy Adult and Adolescent Volunteers Enrolled in Preventive Vaccine Clinical Trials (September 2007). In the absence of a diagnosis, any clinical safety laboratory test result that meets the definition of an SAE as determined by the investigator (e.g., life-threatening) must be reported as an SAE.

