**Table 5: Grading scale to grade the severity of abnormal clinical safety laboratory test results reported as AEs**

Parameter	Grade 1 (Mild)	Grade 2 (Moderate)	Grade 3 (Severe)
Hemoglobin [Female] (g/dL)	11.0 – 12.0	9.5 – 10.9	< 9.5
Hemoglobin [Female] change from baseline value (g/dL)	Any decrease – 1.5	1.6 – 2.0	> 2.0
Hemoglobin [Male] (g/dL)	12.5 – 13.5	10.5 – 12.4	< 10.5
Hemoglobin [Male] change from baseline value (g/dL)	Any decrease – 1.5	1.6 – 2.0	> 2.0
WBC Increase (cell/mm  )	10,800 – 15,000	15,001 – 20,000	> 20,000
WBC Decrease (cell/mm  )	2,500 – 3,500	1,500 – 2,499	< 1,500
Lymphocytes Decrease (cell/mm  )	750 – 1,000	500 – 749	< 500
Neutrophils Decrease (cell/mm  )	1,500 – 2,000	1,000 – 1,499	< 1,000
Eosinophils (cell/mm  )	650 – 1,500	1,501 – 5,000	> 5,000
Platelets Decreased (cell/mm  )	125,000 – 140,000	100,000 – 124,000	< 100,000
Creatinine (mg/dL)	1.5 – 1.7	1.8 – 2.0	> 2.0
ALT increase by factor	1.1 – 2.5 x ULN*	> 2.5 – 5.0 x ULN*	> 5.0 x ULN*
Total bilirubin increase by factor	1.1 – 1.5 x ULN*	> 1.5 – 2.0 x ULN*	> 2.0 x ULN*

\*ULN = upper limit of normal

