## 8.6 General Guidance on Recording Adverse Events

To improve the quality and precision of acquired AE data, the investigator should observe the following guidelines:

- AEs must be assessed for severity (graded) and causality and reviewed by the site investigator.
- If an AE (e.g., low hemoglobin) meets the criteria for two different severity grades simultaneously (e.g., Grade 1 for absolute hemoglobin level and Grade 2 for change from baseline value), the severity grade reported should be the most severe grade (i.e., Grade 2 in the example provided).
- Whenever possible, use recognized medical terms when recording AEs on the AE CRF. Do not use colloquialisms or abbreviations.
- If known, record the diagnosis (i.e., disease or syndrome) rather than component signs, symptoms and laboratory values (e.g., record congestive heart failure rather than dyspnea, rales, and cyanosis); however signs and symptoms that are considered unrelated to an encountered syndrome or disease should be recorded as individual AEs (e.g., if congestive heart failure and severe headache are observed at the same time, each event should be recorded as an individual AE).
- AEs occurring secondary to other events (e.g., sequelae) should be identified by the primary cause. A “primary” AE, if clearly identifiable, generally represents the most accurate clinical term to record. If a primary serious AE (SAE) is recorded, events occurring secondary to the primary event should be described in the narrative description of the case. For example:

Orthostatic hypotension® Fainting and fall to floor® Head trauma® Neck pain

The primary AE is orthostatic hypotension.

- Death is an outcome of an event. The event that resulted in the death should be recorded and reported on the SAE CRF.
- For hospitalizations for surgical or diagnostic procedures, the illness leading to the surgical or diagnostic procedure should be recorded as the SAE, not the procedure itself. The procedure should be captured in the case narrative as part of the action taken in response to the illness.
- Pregnancies that occur in study participants are not considered AEs and will be recorded on a separate Pregnancy CRF. Pregnancy outcomes that include spontaneous abortion, stillbirth or any congenital anomaly must be reported as SAEs.

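### Section 11.5.5.3 grades every laboratory value by Table 5, whose change rows make any hemoglobin fall Grade 1, so about 43-47% of unaffected participants would count as having a Day 8 hemoglobin abnormality

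*Protocol*

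**What the plan says.** Three parts of the protocol bear on this.

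- **Scope of Table 5.** Section 8.3 introduces the table with "The severity of abnormal clinical safety laboratory test results reported as AEs will be graded". Section 8.1.1 adds the filter that comes first: in the absence of a diagnosis, "abnormal clinical safety laboratory test results that are assessed by the investigator to be clinically significant will be reported as an AE".
- **Content of Table 5.** Hemoglobin has an absolute row and a change-from-baseline row for each sex. The change rows are the same for women and men: Grade 1 is "Any decrease – 1.5" g/dL, Grade 2 is 1.6 to 2.0 and Grade 3 is above 2.0. None requires a low value. When the two rows disagree, section 8.6 says that "the severity grade reported should be the most severe grade".
- **Use in the analysis.** Section 11.5.5.3 says "Clinical safety laboratory test values will be evaluated according to the table for grading the severity of adverse events provided in this protocol". It turns to laboratory normal ranges only for parameters that have no toxicity grades, and hemoglobin has them. The graded results then feed the tables by grade, the maximum post-baseline grade per participant and parameter, the shift table, and the rows for "any post-baseline abnormality across visits within parameters, as well as across parameters and visits".

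Section 6.2.2 fixes the reference value: "the Day 1 test results will be used as baseline for analyses". Section 7.2 has the blood count "performed at screening, and at Day 1 and Day 8 visits", so Day 8 is the only scheduled post-baseline value.

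**The concern.** Where the investigator has already judged a result clinically significant, a Grade 1 band that starts at any decrease does no harm: it only assigns a severity to something already called an event. Section 11.5.5.3 takes the same band without the filter and applies it to every Day 8 hemoglobin. A man who goes from 15.0 to 14.9 g/dL becomes a Grade 1 abnormality, although 14.9 is well above the absolute male Grade 1 range of 12.5 to 13.5.

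In a first-in-human study with safety as its primary objective, the hemoglobin abnormality lines and the overall any-abnormality row would then mostly report measurement and biological variation. A reader of the study report would see an abnormality rate near one half that carries no information about the vaccine.

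**Working it through.** The protocol gives no expected rate of hemoglobin abnormalities, so there is no figure of its own to reproduce.

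**Inputs from the protocol.** Grade 1 is any decrease from a single Day 1 value, there is one post-baseline value (Day 8), and all values are graded. Section 11.5.5 pools groups within type. With the schema maxima that gives 20 + 50 = 70 nOPV and 20 + 25 = 45 mOPV recipients per type.

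**Assumptions not in the protocol.** Results are reported to 0.1 g/dL, the Day 1 to Day 8 change is Normal with SD 0.3 to 0.7 g/dL, and the vaccine has no effect.

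**Step 1: chance of any decrease.** A reported fall of at least 0.1 needs a change below -0.05, so P = Φ((-0.05 - μ)/SD), where μ is the mean shift.

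| SD of change | μ = 0 | μ = -0.1 |
|---|---|---|
| 0.3 | Φ(-0.167) = 43.4% | Φ(0.167) = 56.6% |
| 0.5 | Φ(-0.100) = 46.0% | Φ(0.100) = 54.0% |
| 0.7 | Φ(-0.071) = 47.2% | Φ(0.071) = 52.8% |

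The no-shift result is close to a symmetry argument: a fall is as likely as a rise, and ties take the rate a little below one half. A separate simulation that rounds both readings (SD of a single reading 0.2 to 0.6 g/dL, no shift) gives 43.0% to 47.7%.

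**Step 2: counts.** At 43.4% to 47.2%, about 30 to 33 of 70 pooled nOPV recipients and 20 to 21 of 45 pooled mOPV recipients would be flagged by chance.

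**Step 3: which grade.** With no shift, a fall of 1.6 or more (Grade 2 or higher) has probability Φ(-1.55/SD): 0.1% at SD 0.5 and 1.3% at SD 0.7. A fall above 2.0 (Grade 3) has Φ(-2.05/0.7), about 0.2%, at the widest SD. The excess is almost wholly Grade 1.

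**Step 4: the across-parameter row.** Take a 46% chance hemoglobin flag, independent of the other parameters, and suppose purely for illustration that 10% and 25% of two arms have an abnormality elsewhere.

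- 1 - (0.90 × 0.54) = 51.4%
- 1 - (0.75 × 0.54) = 59.5%

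A 15-point difference appears as 8.1 points, that is 15 × 0.54.

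**Step 5: the shift table.** Day 1 is the reference, so it has no change from baseline and can be classed only by the absolute row. Day 8 can be classed by either row. A participant whose level is unchanged apart from noise therefore moves from ungraded to Grade 1 nearly half the time. The any-abnormality rows at baseline and after it are not comparable for the same reason.

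**Step 6: after the fix.** This was simulated with an equal sex mix, mean hemoglobin 13.0 to 13.5 g/dL in women and 14.7 to 15.2 in men, between-person SD 0.8 to 1.0 and reading SD 0.3 to 0.5, all assumed. As written, 46% to 52% have some hemoglobin grade by either row. Counting an absolute grade or a fall of at least 1.6 gives 4% to 16%. The lower-limit-of-normal clause is not modelled, because the limits belong to the site laboratories.

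**The case against.** The best defence has four parts.

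- **The literal reading may not be intended, and the SAP may settle it.** Section 11.5.5.3 summarizes abnormalities, and a normal-range value need not be one. Section 8.6 is guidance on recording AEs, and section 11.5.1 promises more detail in the SAP. This shows that the authors may not have meant the result. It does not undo the stated rule, which sends every graded parameter to Table 5. Section 8.6 also shows that the change row was meant to be able to set a grade.
- **The reach is limited.** This stands. A reader might infer that all maximum-grade summaries are swamped or that an ALT, neutrophil or platelet signal would be hidden. The documents do not support that: maximum grade is tabulated per parameter, and each parameter keeps its own grades, values, changes, shift table and boxplots.
- **No decision or test is compromised.** This also stands. The primary endpoint counts clinically significant Day 8 values reported as AEs. The pause rules in section 9.3 concern SAEs and Grade 3 events not reasonably attributable to another cause. No test of laboratory abnormalities is planned, so the dilution in Step 4 illustrates how the row reads and is not lost power. Chance flags fall on both vaccines alike, so the comparison is diluted and not biased.
- **The table is adapted from an FDA toxicity scale.** Using a recognized scale is reasonable. The difficulty is its use outside the scope that section 8.3 gives it.

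Two further inferences should be resisted. One is that the 15 mL Day 1 draw makes a fall by Day 8 expected: the protocol gives no such figure, and the point does not need it. The other is that chance Grade 3 falls would be common: Step 3 puts them at about 0.2% even at the widest SD.

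**Conclusion.** The point holds, within limits. With no vaccine effect and no mean shift, the stated rule labels about 43-47% of participants as having a Day 8 hemoglobin abnormality. The assumed SD of 0.3 to 0.7 g/dL hardly matters; a mean fall of 0.1 g/dL would raise the rate to 53-57%. What is damaged is the hemoglobin by-grade, maximum-grade and any-abnormality lines, the hemoglobin shift table, and the single row that pools all parameters. It is a matter of interpretability in the safety report. It deserves correction because the rule is written into the protocol and contradicts the scope that the protocol itself gives Table 5.

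**What to change.** In section 11.5.5.3, and in the SAP to match:

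1. Tabulate the hemoglobin change-from-baseline grades in a row of their own.
2. In the hemoglobin by-grade, maximum-grade, any-abnormality and shift summaries, and in the across-parameter row, do not count a Grade 1 change-from-baseline result as an abnormality unless the Day 8 absolute value is also graded in Table 5 or is below the laboratory's lower limit of normal.
3. Keep Grade 2 and Grade 3 change-from-baseline results in all summaries. They are rare by chance, and dropping them would hide large falls that end within the normal range.
4. Leave Table 5 as it is for results reported as AEs.

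The cost is a short addition to the text and one table row, with no new data. The downside is that small falls within the normal range appear only in the separate change row and in the continuous change-from-baseline summaries.
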